3.6. Data Collection

3.6.a Monitoring Visits and Surveys: The data collection schedule includes visits every 3 months: every other visit (every 6-months) will include a comprehensive survey (see Figure 2); all surveys are interviewer-administered on encrypted study tablets. At enrollment, participants will provide informed consent and then respond to the first (baseline) comprehensive survey. Participants will complete two additional comprehensive surveys (interim and endline) during the main trial phase. During the delayed intervention phase all participants will respond to an additional interim survey and wait-list control participants will also respond to a final (endline) survey at the end of the period. Comprehensive surveys will assess hypothesized covariates and mediators of our primary and secondary outcomes (see Table 3). Brief monitoring surveys (15 minute) to record outcomes at 3-month intervals will capture: self-reported HIV risk behaviors and risk reduction practices (condom use or partner reduction); HIV testing; PrEP use (including refills and adherence); other prevention services sought and utilized (STI testing and treatment, harm reduction). The endline survey will include questions about engagement in study activities and interactions with navigators. We utilize measures that have been validated in Brazil when possible, including those we have used in prior studies and those we are currently validating in Trans Amigas (see Measures section 3.7 for more detail). Participants will be reimbursed for all study visits.

Participants may choose to schedule visits at any of the three project sites, to optimize convenience. For those on PrEP, data collection visits will be scheduled at the participant's clinic to ensure that PrEP distribution, HIV testing, DBS collection, and survey data collection is integrated efficiently into clinical care. Study staff will be available at each site. For participants with difficulty presenting at a study location, staff will offer interviews by phone or WhatsApp, to minimize missing data, though all attempts will be made to maximize in-person data collection. Interviewers will be trained on interviewing techniques, standard operating procedures, and human subjects research, including ensuring complete confidentiality. (See Form E, Human Subjects for details).

3.6.b PrEP Data Extraction: Data regarding PrEP use, which became available nationally for at-risk populations in December 2017, will be extracted from the national SICLOM (Sistema de Controle Logístico de Medicamentos) database, which captures all ARV distribution nationally. PrEP dispensing will be extracted quarterly from SICLOM and stored securely, including visit dates, pill count and dose, and any associated observations. We will utilize clinical records at the facilities to note visits for other purposes, including visits related to PrEP side effects (see 3.6.c below). The investigators have successfully utilized SICLOM for extraction of medication dispensing information in the Trans Amigas project.

3.6.c Clinic data extraction: Clinic-based HIV testing data and uptake of clinic-based prevention services, including STI testing and treatment, sexual health counseling, and HIV care visits (for those who seroconvert) will be extracted bi-annually, including visit purpose, dates, services received, HIV test result, and associated observations. Data from participant clinical files will be extracted electronically and uploaded to a secure data base kept by the study data managers (see Form E Human Subjects for details). Our team has successfully and safely extracted clinical data for Trans Amigas participants at the CRT and will utilize similar protocols.

3.6.d Drug Concentration Testing: Drug concentrations in the blood have emerged as strong correlates of protection in PrEP trials, accounting for the majority of the variation in PrEP benefits. Dried blood spots (DBS) are easy to collect, require no processing in the field, are easy to store and ship, and are feasible for monitoring drug concentrations among trans women in our current PrEP demonstration project. The DBS will be collected at the clinical sites at each visit for PrEP dispensation by trained staff and processed in accordance with procedures developed for previous studies. (Investigators have all utilized DBS for drug concentrations in previous studies). Staff will use a medium gauge lancet to puncture the fingertip and extract

whole blood onto filter paper, to be dried on a storage rack prior to placing the DBS in individual plastic zip lock bags with a desiccant packet and humidity indicator. DBS will be temporarily stored at each clinic in a freezer at -4C, then batch shipped monthly to the local laboratory for storage at -20C and batch tested quarterly using a validated method for quantification of drug concentrations of tenofovir and emtricitabine⁹⁰. Adherence will be defined as having drug concentrations at levels required for protection (≥ 4 pills per week)⁹¹.

3.6.e Intervention Monitoring. We will monitor intervention quality and fidelity using strategies from Trans Amigas, including a group session form (GSF) and a peer contact form (PCF). GCFs will record attendance using participant ID, date, and content and activities completed in each group session, and note distribution of HIVST to each participant in each session. PCFs are designed to track PNs' protocol-guided interactions with participants, noting each successful or attempted in-person navigation meeting, phone call, or text message. On PCFs, PNs note the date of contact, participant IDs, the topics discussed, and any required follow-up. Forms are entered into a database to monitor group session fidelity and track navigation contact over time. Each PN will meet weekly with the study coordinator to debrief intervention content and interactions with participants and to submit completed forms. The study coordinator will participate on weekly calls with the investigators to discuss client challenges or PN performance problems, re-training needs, and any modification or adaptation required to improve study processes. Investigators will review monitoring data on monthly calls.

3.6.f Qualitative interviews. We will conduct semi-structured in-depth qualitative interviews (IDIs) with 18 intervention participants at two time points (36 total IDIs). We aim to conduct one interview at the beginning of group sessions and one at the conclusion of peer navigation. PNs will identify participants who are early adopters or decliners of HIVST and/or PrEP (uptake or decline within the first two to three group sessions) and refer them for qualitative interviewing. If the participant is interested, the PN will describe the interview procedures and schedule an appointment. Qualitative interviews will be conducted in-person by a trained interviewer, supervised by co-I [name]. Interviews will last approximately 1 hour, will be audio recorded, and will explore uptake/declination of and persistence with prevention tools in the context of the conceptual framework using probes specifically related to the intersectional stigma domains of interest: internalized, anticipated, and enacted stigma related to gender identity, race, HIV, PrEP, and other stigmas associated with marginalized social positions and behaviors (e.g. sex work, drug use), as well as stigma resilience. The structured interview guide will allow for organic exploration of additional emergent stigma domains, as appropriate, and explore how participants perceive intersections in identity-based stigma, social position-based stigma, and stigma related barriers to prevention and the impact of the intervention on stigma resilience.

3.7 Measures

Primary Exposure: Randomization arm – intervention or wait-list control – will be considered the primary predictor variable for all primary analyses and recorded on study enrollment forms. Because the degree of engagement with the intervention will vary by individual, we will also capture intervention dose on study monitoring forms as a secondary exposure measure for additional (per protocol) analyses.

Primary Outcomes: (Evaluation: Aims 1 & 2): HIV testing uptake will be defined as any clinical evidence or report of HIV testing in each interval. This includes multiple data sources: documented HIV testing at a study clinic, report of having attended a non-study clinic for HIV testing, or evidence of HIVST kit receipt with self-report of HIVST use and/or documented HIVST use by the PN during a group or individual navigation session. The primary PrEP use outcome measure is PrEP *persistence*, which is the PrEP measure utilized for sample size calculations. We will document *PrEP initiation*, defined as a participant filling their first PrEP prescription, through PrEP dispensing information in the national SICLOM database. However, because initiation does not imply continued use, we will focus analyses of PrEP use on *PrEP persistence* – or documented use at every interval, defined as sufficient pill dispensation for complete 3-month coverage with no more than 10 days uncovered in the period. Secondary outcomes, including PrEP *adherence* and uptake of other prevention services (harm reduction, STI care) are listed in Table 3, below.

Mediators: Intersectional Stigma: We will include a comprehensive suite of stigma measures that will be examined together in mediation and moderation analyses (see Analysis section 3.8). To explore the concept of intersectional stigma, we will analyze potential interactions between the stigma domains. This reflects the concept of intersectionality as more than an additive process of multiple stigmatized identities, but where experiences of multiple types of stigma create a confluence of interlocking systems of oppression that act synergistically as barriers to prevention and cannot be meaningfully interpreted independently. We will include quantitative measures of internalized, anticipated, and enacted stigma in the following domains: gender-related stigma, race-related stigma, stigma related to sex work and substance use, HIV and PrEP stigma. Stigma resilience is operationalized as coping self-efficacy and healthcare empowerment in the context of anticipated

and enacted stigma. Comprehensive surveys will be conducted at enrollment, interim, and endline at 6-month intervals; we do not expect changes in stigma every 3 months (interval for outcomes monitoring).

Covariates: We will measure demographic and other individual, social, and structural barriers or facilitators to care to assess potential covariates and confounders in analyses.

Table 3: Primary and Secondary Measures

Domain	Instrument/measure	Data source	Frequency of data collection/extraction
PRIMARY EXPOSURE			
Intervention	Randomization arm	Enrollment/study records	Continuous during enrollment
PRIMARY OUTCOMES			
HIV testing	Binary: Tested (HIVST or at a clinic) in past 3-months	Clinical data extraction; study records (HIVST); self-report (testing)	Extracted bi-annually, Continuous, Monitoring visits (3-monthly)
PrEP initiation	Binary: Initiation of PrEP in past 3-months*	National data (SICLOM)	Extract quarterly
PrEP persistence	Binary: PrEP dispensed with 80 or more days covered in 3-months per dispensation records*	National data (SICLOM)	Extract quarterly
SECONDARY OUTCOMES			
Prevention and service uptake	Uptake of harm reduction services	Self-report	Monitoring visits (3-monthly)
	STI referrals and treatment	Clinical data extraction; Self-report	Extracted bi-annually, Monitoring visits (3-monthly)
	Condom use (consistent use with regular and occasional partners and clients)	Clinical data extraction; Self-report	Extracted bi-annually, Monitoring visits (3-monthly)
PrEP adherence	Drug levels	Dried blood spots	Monitoring visits (3-monthly)
SECONDARY EXPOSURE			
Intervention dose	Engagement with intervention (group sessions & navigation)	Study monitoring forms	Continuous
COVARIATES/MEDIATORS			
Demographics	Age, gender identity, SES, race, housing stability, mobility, employment, sex work	Self-report - Surveys	Comprehensive visits (6-monthly)
Intersectional stigma	Internalized, anticipated, and enacted stigma related to: Identity-based stigma: gender ⁹² , race ⁹³ Social position-based stigma: sex work ⁹⁴ , substance use Stigma-related barriers: HIV stigma ⁹⁵ , PrEP stigma ⁹⁶	Self-report - Surveys	Comprehensive visits (6-monthly)
	Stigma resilience: Coping self-efficacy ⁹⁷⁻⁹⁹ Healthcare empowerment ¹⁰⁰	Self-report - Surveys	Comprehensive visits (6-monthly)
Gender affirmation	Need for and experiences of gender affirmation ¹² Transgender group identity ⁹²	Self-report - Surveys	Comprehensive visits (6-monthly)
Social, structural barriers to / facilitators of prevention	Depression ¹⁰¹⁻¹⁰³ , substance use ¹⁰⁴ , social support ^{105,106} , social cohesion ^{107,108} , relationship violence ¹⁰⁹ , trauma ¹¹⁰ , access to clinical care and services received, food insecurity ^{111,112} .	Self-report - Surveys	Comprehensive visits (6-monthly)

*calculated among those with indications for PrEP use.

3.8 Data Analysis Plan and Statistical Procedures:

Preliminary analyses, missing data. Frequency tables for all variables and measures of central tendency and variability for continuous variables (e.g., stigma scores) will characterize the sample and will be stratified by randomization arm to check for imbalances. If arms differ significantly at baseline on one or more covariates, we will use causal modeling methods (e.g., propensity scores, targeted maximum likelihood estimation) to obtain the desired marginal effect estimates under the counterfactual assumption of balanced arms¹¹³⁻¹¹⁷. We will address incomplete data with multiple imputation (MI)¹¹⁸; MI makes the relatively mild assumption that incomplete data arise from a conditionally missing-at-random (MAR) mechanism¹¹⁹. Auxiliary variables will be included to help meet the MAR assumption^{120,121} and sensitivity analyses will be conducted with weighted MI¹²² to assess the robustness of the MAR assumption¹²³. SAS¹²⁴ and *Mplus*¹²⁵ will be used for analyses.

Primary analyses for Aims 1 and 2. We expect HIV prevention outcomes to improve in the intervention arm relative to the control arm during the main trial phase. We hypothesize that, following the intervention, odds of HIV testing will be higher for intervention participants relative to control participants (Aim 1, Hypothesis 1). We also hypothesize that, following the intervention, the odds of PrEP initiation and persistence will be higher for the intervention group than for the control group (Aim 2, Hypothesis 2). Our primary interest is to estimate the marginal or population-average effects of intervention participation on these primary outcomes rather than the effect for a hypothetical average subject¹²⁶. Moreover, within-subject outcome correlations are considered nuisance parameters rather than quantities of interest to be modeled explicitly. Accordingly, generalized estimating equations (GEE) will be used for the primary analyses to test Hypotheses 1 and 2 using time-averaged comparisons of post-baseline (follow-up) measurements of intervention group with control group in the main trial phase. Alpha (α) will be set at .05 for these two planned comparisons. The alternating logistic

regression (ALR) approach implemented in SAS PROC GENMOD will be used to address the 3-level clustering of observations within participants and participants assigned to *Guerreiras* group leaders. This analysis will follow an intent-to-treat (ITT) approach by including all randomized participants. Further detail on the analytic model and secondary analyses, including secondary outcomes, intervention persistence, and intervention replicability, are included in Form E, Statistical Design and Power.

Primary Analyses for Aim 3. GEE will be used to test Aim 3 hypotheses that, following the intervention, relative to the control arm, intervention arm participants will have: 1) higher mean levels of resilience to anticipated stigma, 2) higher mean levels of resilience to enacted stigma, and 3) lower mean levels of internalized stigma. Analyses will follow the same ITT modeling approach as described above for Aims 1 and 2, except that a normal distribution and identity link will be employed to analyze continuous, normally-distributed stigma scores. These hypotheses will be tested via planned time-averaged comparisons of post-baseline measurements of the two arms in the main trial phase. These comparisons will be tested at $\alpha=.05$ per comparison.

We will also explore whether stigma measures at interim (six-months) surveys mediate the relationship between intervention assignment and subsequent outcomes as well as whether combinations of stigmas measures at baseline and six-months act synergistically (interact) and moderate the exposure-outcome associations in order to assess intersectional stigma. We will also assess whether measures of gender affirmation and transgender group identity increase over the course of the intervention and mediate the relationship between intervention arm and subsequent outcomes. Further detail on Aim 3 secondary analyses, including mediation and moderation, are in Form E, Statistical Design and Power.

Statistical power. We computed minimum detectable effect sizes for primary outcomes using the two-group repeated proportions module in NCSS PASS 16¹²⁷. The study will begin with 400 participants equally allocated to two study groups. Assuming 25% attrition, data from 300 participants will be available for analysis at all time points. We further lowered the effective sample size (ESS) to account for correlations between participants receiving the intervention from the same *Guerreiras* PN pairs, using a range of plausible intraclass correlations (ICC)s within PN pairs. Assuming $\alpha=.05$ and $\text{power}=.80$, with four post-baseline measurements and assuming control group proportions $P_0=.50$ for HIV testing and $P_0=.05$ for PrEP use, we will have sufficient power to detect small to medium effects. This includes effects as low as 13% and 8% difference in proportion in HIV testing and persistent PrEP use, respectively, in the intervention arm compared to control. Effect size estimates for primary analyses (all Aims 1, 2, and 3) fall between cutoffs of .20 and .50 for small and medium standardized effect sizes¹²⁸. Statistical power is fully elaborated in Form E, Statistical Design and Power.

Qualitative data analysis: We will optimize the longitudinal qualitative data we are collecting through best practices for analysis of this type of data, including tracking coding and analysis decisions over an extended analysis period, establishing clear coding and review processes, and using concept mapping to track codes, relationships between codes, and thematic groupings¹²⁹. Audio-recordings will be transcribed; transcriptions will be managed using Atlas.ti, software designed to assist with textual datasets¹³⁰. Functions include assisting with indexing, coding, searching, and mapping. Guided by gender affirmation theory and the lens of intersectional stigma, we will approach the qualitative analyses with the aim of elucidating how relationships of power or disadvantage based on stigma related to gender, race, social position (e.g. sex work, substance use), and stigma-related barriers (e.g. HIV and PrEP stigma) operate as mutually reinforcing rather than distinct systems of oppression, how these social and structural processes evolve over time and within the context of the intervention¹³¹. MPI [name] and Co-I [name] will independently review the transcripts, beginning with analyzing cross-sectional baseline data separately and then grouping interviews by participant at endline to reflect temporality of experiences within each participant. Investigators will identify prospective codes with particular attention to interactions between and nesting within codes, highlighting intersections of identities and social processes over time. We will draft evolving summaries, including key insights and supporting data, and will convene weekly to discuss interpretations and arrive at consensus on key themes, navigating evolving interpretations over time through concept mapping with periodic coding review¹²⁹.

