Navigation (for 6 mos post-groups)	Staying Connected / Permanecendo Ligada	Provide one-on-one individualized support for navigating current healthcare system, reinforcing concepts from group work, including problem-solving and strategies for coping with anticipated and enacted stigma

3.4.b. HIV self-testing and/or navigation to clinic-based testing. HIV self-testing (HIVST) will be introduced and demonstrated in session 1 and will be made consistently available to all *Guerreiras* participants for free through our public sector partnerships. HIVST is available in Brazil in the public sector⁸⁵. PNs will bring HIVST kits to each session; *Guerreiras* participants will have the option of utilizing HIVST in groups, with their PN, or on their own. At each group session participants will be invited to debrief their HIVST experience with the group if they so choose. PNs will offer one-on-one support for HIVST before and after each group session as needed and will offer navigation to clinic-based HIV testing to those who prefer clinic-based testing. PNs will be trained in test counseling to ensure they are prepared to debrief test results, though very few social harms have been reported in HIVST studies with vulnerable populations^{71,86,87}. PNs will record HIVST distribution and tests conducted with them or in the group on standardized case report forms (see section 3.6.e).

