of the last participant in a block. For participants allocated to intervention, assignment to a *Guerreiras* group will occur as soon as there is sufficient enrollment to form a group.

3.5.d. Retention: Upon enrollment, participants will be asked to provide contact information, including address, cell phone/WhatsApp number, other social media contacts, and also to volunteer up to three individuals who can contact them should study staff be unable to do so. At each 3-month monitoring visit, staff will validate contact information in addition to completing data collection (see section 3.6.a & 3.6.b). The Brazilian study team has experience with these contact methods in retaining Trans*National and Trans Amigas study participants. (See Form E, Recruitment and Retention for further details on retention plans). Given the mobility and often unstable housing trans women experience, we expect to retain 75% of the cohort. To date just over 50% of Trans*National participants (an observational study) and just over 80% of Trans Amigas participants (an intervention study with consistent contact) have been retained; as a result, we believe retention will be closer to Trans Amigas retention rates. We account for attrition in the statistical power (see section 3.8).

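### HIV testing is ascertained differently by arm in quarters with no interview, because navigator forms exist only in the intervention arm and no scoring rule covers a missed visit

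*Combined protocol and SAP*

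**What the plan says.** Section 3.7 (Primary Outcomes) states: "HIV testing uptake will be defined as any clinical evidence or report of HIV testing in each interval". The accepted evidence is a documented test at a study clinic, a participant's report of testing at a non-study clinic, or, for self-tests, "evidence of HIVST kit receipt with self-report of HIVST use and/or documented HIVST use by the PN during a group or individual navigation session". Table 3 words the same outcome as "Binary: Tested (HIVST or at a clinic) in past 3-months".

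The sources work on different terms:

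- **Study-clinic records** are extracted twice a year with dates and results (3.6.c), in both arms, whether or not the study visit took place.
- **Navigator and group forms**: "PNs will record HIVST distribution and tests conducted with them or in the group on standardized case report forms" (3.4.b). They are submitted weekly (3.6.e). Controls have no navigator until after the one-year wait (3.3.a), so in the main trial phase these forms exist in one arm only.
- **Interviews** every three months are the only source for off-site tests and for kits used without a navigator present.

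On missing data, section 3.5.d says "we expect to retain 75% of the cohort", and 3.6.a offers phone or WhatsApp interviews to those who cannot attend. Section 3.8 plans multiple imputation, saying that "MI makes the relatively mild assumption that incomplete data arise from a conditionally missing-at-random" mechanism. It adds auxiliary variables and a weighted-MI sensitivity analysis. Nothing in the supplied text says how a quarter is scored when its interview is missed.

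**The concern.** A completed interview can return either answer. A record can only return tested: its absence does not exclude an off-site test or an unsupervised self-test. So once the interview is missed, the evidence that remains is one-sided, and the intervention arm has one more source of it.

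Both natural ways of handling such a quarter go wrong:

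- **Record counts as tested, otherwise missing and imputed.** Every observed uninterviewed quarter is then a yes. Whether a quarter is observed depends on its own value and on arm, which is not missing at random.
- **Record counts as tested, otherwise not tested.** Real tests are lost in both arms, and more are lost in the arm with fewer record sources.

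Either way the primary Aim 1 contrast can differ from zero when testing is identical in the two arms. Because the rule is not stated, it could also be chosen after the data are seen.

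**Working it through.** **Plan's own figures.** 400 × 0.75 = 300 analysable, 150 per arm, as section 3.8 states. The 13-point detectable difference (control 50%, four post-baseline measurements, alpha .05, power .80) needs a within-person correlation and a navigator-pair ICC. The supplied text gives neither, so the figure can only be bracketed. With 8 pairs (16 navigators) of about 19 retained participants and a two-sided test, it corresponds to a correlation of .54 at ICC 0, .41 at .01, .31 at .02 and .13 at .05. It is plausible. It implies a standard error of .13/(1.96 + 0.84) = .0464.

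**Notation.** p = true testing rate; m = share of quarters with no interview; s = share of true tests in those quarters that records capture. Subscripts 1 and 0 denote intervention and control. p = .50 in both arms (the plan's control rate, no true effect). The values of s are assumptions; the documents give none.

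**Formulas for the proportion an arm would show**

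- Blanks imputed at the arm's observed rate: [p(1−m) + mps] / [(1−m) + mps]
- Blanks scored no: p(1−m) + mps

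**Case A: 25% of every visit missed in both arms, s = .6 versus .3**

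- Imputed: .450/.825 = .5455 versus .4125/.7875 = .5238, difference **+2.2 points**. With the standard error above, the two-sided false-positive rate is about 7.5%.
- Scored no: .450 versus .4125, difference **+3.8 points**, false-positive rate about 13%.

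**Case B: loss builds evenly, with navigator capture ending early.** Missed shares are 6.25%, 12.5%, 18.75% and 25% at months 3, 6, 9 and 12 (mean 15.6%). Groups last 6–8 weeks and navigation six months, so navigator forms end at about month 8 if groups form promptly. Set s = .6 versus .3 for three quarters and .3 in both arms for the last.

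- Imputed: differences of .0049, .0101, .0156 and 0; mean **+0.8 points**, false-positive rate about 5.3%.
- Scored no: .15 × m gives .0094, .0188, .0281 and 0; mean **+1.4 points**, false-positive rate about 6.1%.

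**Sensitivity to capture (25% missed in both arms, imputed).** s = .5 versus .3 gives +1.5 points; .8 versus .3 gives +3.5; the extreme 1 versus 0 gives +7.1; equal capture gives 0.

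**Sensitivity to unequal missed visits (s = .6 versus .3)**

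| Missed, intervention / control | Imputed | Scored no |
|---|---|---|
| 25% / 25% | +2.2 | +3.8 |
| 20% / 30% | +0.5 | +6.5 |
| 15% / 35% | −1.2 | +9.25 |
| 20% / 50% | −3.0 | +13.5 |

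Under imputation with equal p, the bias is upward only if m₁s₁/(1−m₁) exceeds m₀s₀/(1−m₀). That needs s₁/s₀ above 1.7, 3.1 and 4.0 in the last three rows. The last row takes its loss rates from the two precedents in 3.5.d (just over 80% and just over 50% retained). They come from other studies and are not forecasts by arm.

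**With the fix.** If only interviewed quarters count as observed and the rest are imputed, and data are missing at random given attendance, both arms return .500 and the bias is 0.

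**The case against.** The other side has several sound points.

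- **Direction.** A reader might infer that the flaw always inflates the Aim 1 effect. It does not: under imputation the sign reverses if controls miss enough more visits. Upward bias holds in all four rows only when blanks are scored no.
- **Never a no.** A reader might infer that a missed visit can be filled as tested but never as not tested. The any-evidence wording, read literally, also permits no evidence to be scored as not tested. The plan leaves this open.
- **Look-back.** A reader might infer that the next interview never asks about a skipped quarter. That rests on a Table 3 label. The text of 3.7 says each interval, and the questionnaire is not in the documents.
- **Size.** The 25% is cohort attrition, not the share missed at each visit, and navigation ends before month 12 if groups form promptly. Women who miss study visits may also be out of contact with navigators, and the precedent in 3.1.b is monthly contact for 70%. All of this narrows the capture gap, so Case B is the fairer central illustration, although its dropout pattern is itself assumed.
- **Safeguards.** Remote interviews reduce missed visits, and auxiliary variables and weighted MI probe the missing-at-random assumption. None of them defines the scoring or targets a record source held by one arm. Section 3.8 defers model detail to Form E, which was not available; it may address this.

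A self-test done with a navigator is a genuine outcome. The problem is only that equivalent tests in controls have less chance of being recorded.

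**Conclusion.** The concern stands in a bounded form. The any-evidence rule, combined with a record source held by one arm, makes ascertainment in uninterviewed quarters depend on arm, and the planned imputation does not correct that. It probably favours the intervention, by roughly 1 to 4 points in the illustrations with equal loss and 60% versus 30% capture, against a 13-point target. The imputed version can turn negative if controls miss more visits. These sizes rest on assumed capture rates and dropout patterns; the documents support the mechanism but do not fix its magnitude.

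The issue does not by itself overturn a 13-point effect. It does raise the error rate on a primary outcome, and the choice of scoring rule moves the estimate, so the rule should be set in advance.

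**What to change.** 1. **Survey item.** Ask about testing since the last completed visit, with the month of each test, and reconcile Table 3 with the text of 3.7. Later visits can then recover skipped quarters. This does not help permanent dropouts.
2. **Primary analysis.** Treat a quarter as observed only if a completed interview (in person, phone or WhatsApp) covers it. Otherwise set it missing in both arms, whatever the clinic or navigator forms show, and impute.
3. **Sensitivity and reporting.** Run any-evidence scoring as a sensitivity analysis, stating how blanks are handled, and report capture by source and arm.

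An analysis restricted to study-clinic records should not be offered as a comparison on equal terms. Navigators both steer participants to clinics and supply self-tests that may replace clinic tests, and it would drop self-testing, a core part of the outcome.

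The cost is one reworded survey item, a short addition to section 3.8 and one sensitivity analysis; the enrolment target of 400 does not change. The downsides are that some documented tests are set aside in the primary analysis, recall over longer gaps is less exact, and the analysis still assumes data are missing at random given interview attendance.
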